- quality of life (QOL), as defined by the COPD Assessment Test (CAT)
- total number of days of antibiotic therapy for AECOPD during follow up
- total number of days of oral steroid therapy for AECOPD during follow up
- type of exacerbation (as they occur (rate over time)):
 - □ defined by Anthonisen criteria
 - defined by a clinical adjudication committee (CAC), who will use sputum, viral and symptom data to determine aetiology of each event

Mechanistic Analyses

BCG vaccine-specific responses comprised of trained immunity, gene expression analyses, cell phenotyping and functional screening.

- Based on analysis of dried blood spot (DBS) samples at baseline, 1, 3, and 12 months:
 - □ anti-BCG antibody responses
 - \Box cytokine profiles (IL-1 β , IL-6, TNF α , IL-10)
- Based on whole blood, dried blood spot (DBS), peripheral blood mononuclear cells (PBMC), neutrophils, serum, and PAXgene tubes at baseline, 1, 3, and 12 months:
 - □ antigen-specific B cell & antibody
 - $\hfill\square$ trained immunity
 - □ serum cytokine analysis
 - □ transcriptomics
 - □ flow cytometry
- Based on sputum, saliva, nasal swab, and DBS samples following exacerbation:
 - □ microbiology profile (multiplex PCR, bacterial culture)
 - anti-pathogen antibody responses (Immunoglobulin G (IgG)/ Immunoglobulin A (IgA))
 - □ anti-BCG antibody responses
 - Cytokine profiles (IL-1, IL-6, TNFα, IL-10)

TRIAL SCHEMA

STABILISE: a multicentre, randomised, parallel group, superiority trial to inveSTigAte the use of BCG vaccine In aLtering Immune reSponse and Exacerbation in chronic obstructive pulmonary disease (COPD)

*Mechanistic subgroup only

[±] Both groups to provide exacerbation samples unless patient opts out

LIST OF CONTENTS

1. BAG	CKGROUND AND RATIONALE

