1.2.2 Justification for design

We have chosen a Prospective Randomised Open Blinded Endpoint (PROBE) design, powered to detect a 20% reduction, equivalent to 0.45 AECOPD/year in patients meeting our inclusion criteria. The primary outcome of the study is medically confirmed exacerbations of airways disease, treated with at least additional oral treatment (antibiotics or steroids); even though this moderate-severe AECOPD definition is a robust outcome commonly used in COPD trials, there is potential for bias to be introduced if the patient or clinician is aware they have received the vaccine. Despite the fact that a double blind design would be the most robust trial design with respect to bias, it have been proven to be exceedingly expensive and difficult to commercially produce matching blinded placebo vials. A PROBE study design maintains the benefits associated with a strict randomisation procedure, while the blinded end points help to eliminate bias. We will employ a group of clinical experts who are not responsible for recruiting participants into the trial to join an adjudication panel to determine the presence or absence of the exacerbation based on several sources of information. By doing this we will ensure that the primary outcome will be undertaken blinded to treatment allocation. Each panel

member will give their diagnosis and where there is disagreement, cases will be resolved by discussion. This addresses the problem of achieving a diagnosis from multiple sources of information and of subjective assessment of that information, as a diagnosis will be confirmed by consensus.

An alternative vaccine was not desirable as the trial concept is that non-specific immunity will be driven by BCG; another vaccine would only be an option if specific immunity were the outcome, or it was well known that an alternative vaccine did not have any non-specific immune priming, which is not the case.

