6.7 Blinding

STABILISE is a PROBE trial and will utilise a Clinical Adjudication Committee (CAC) to assess the primary outcome to determine the number of exacerbations after randomisation using all available trial related clinical information. The adjudication committee will be blinded to the allocated treatment arm. They will look at basic patient details, symptoms of the AECOPD (from the patient), treatment history including any hospital admission (from the GP/medical record/CRF) and the laboratory test results (i.e. the sputum, swab and DBS samples).

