8.2 Main trial outcomes

8.2.1 Primary outcome(s)

The primary outcome is moderate to severe AECOPD rate over 12 months follow up from IMP administration date (or from the date of randomisation if no treatment was administered). This is defined by the clinical adjudication committee and will be based on an assessment of:

- basic patient details
- healthcare utilisation (taking additional antibiotics and/or steroids, as recorded in the medical record, including prescription data),
- patient-reported symptoms of the AECOPD
- laboratory results from patient-provided sputum, saliva, nose/throat swabs and DBS samples following an exacerbation

Severe events are defined by additional hospitalisation. Confirmation of events as stated in section 8.1, will occur via the CAC. Terms of reference for the CAC will be set.

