17.4.3 Tier 3 outcomes (all exacerbations)

All outcomes will be recorded whenever a participant experiences an exacerbation and provides sputum, saliva, nose/throat swabs, and DBS samples.

Anti-BCG antibody responses, as obtained from ELISAs to detect IgG, IgA and IgM responses to whole BCG organism, proteinaceous (Ag85) and a non-proteinaceous (Lipoarabinomannan) antigen

- Cytokines: IL-1B, IL-6, TNFα and IL-10
- Type of pathogen present (bacteria, virus) and specific species
- IgG and IgA response to any identified pathogen

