DBS will be obtained from subjects at the pre-randomisation baseline visit and then at 1, 3 and 12 months post randomisation/vaccination (for the control/BCG vaccine groups respectively). DBS will be collected by capillary sampling onto forensic-grade 226 DBS cards (Ahlstrom Munksjo) with 8 spots collected at each time-point. The eluates from the main study will be obtained from the DBS using our established and standardised methods and soluble factors assessed (44). The eluates will be used to detect changes in anti-BCG antibody responses within individuals, over time by use of our established in-house ELISAs to detect IgG, IgA and IgM responses to whole BCG organism, proteinaceous (Ag85) and a non-proteinaceous (Lipoarabinomannan) antigen. Using this approach, we have shown that anti-BCG responses increase after vaccination (45). From this, we will be able to determine how well subjects respond to the vaccine and correlate these anti-BCG responses to other markers (risk of exacerbation, changes determined in the detailed mechanistic subgroup, exacerbation samples and markers determined from the main study). Eluates will also be used in ELISAs to determine whether baseline levels of cytokines most associated with pro-inflammatory effects (IL-1B, IL-6, TNF) and anti-inflammatory effects (IL-10) are modulated by BCG vaccination. Finally, depending upon what effects are found in studies performed in the mechanistic subgroup and from the exacerbation samples, DBS cards can be revisited, either during the course of this study or subsequently, to examine other effects of BCG vaccination (e.g. additional cytokines, epigenetics and clinical metabolomics).

A1.2 Tier 2 Methods

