This tier is focused on participants who experience an exacerbation and have provided sputum, saliva, nose/throat swabs and DBS samples, and is designed to capture microbiological and immunological information from these participants. PCR for respiratory viruses and standard culture for bacterial pathogens will be performed in United Kingdom Accreditation Service (UKAS)-accredited NHS clinical microbiology laboratories. IgG and IgA responses to any pathogen identified will be assessed in saliva and sputum, in parallel with antibody testing in matched DBS eluates. DBS eluates will be used in assays to determine anti-BCG and cytokines as described in Tier 1. If necessary, eluates will be tested further, based on signatures identified in the detailed mechanistic sub-study.

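### The blinded adjudication committee receives exacerbation DBS results with no exclusion of anti-BCG antibody, so its file can carry a probabilistic marker of allocation

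*Protocol*

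**What the plan says.** **Blinding.** Section 1.2.2 accepts that an open design could introduce bias and answers with an expert panel: "By doing this we will ensure that the primary outcome will be undertaken blinded to treatment allocation". Section 6.7 says the CAC is blinded to arm. Section 18.7 says the same and makes the CAC's determination the primary outcome data.

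**What the CAC sees.** Section 6.7 has it count exacerbations "using all available trial related clinical information", and its itemised list ends with "the laboratory test results (i.e. the sputum, swab and DBS samples". Section 8.2.1, which defines the primary outcome, includes "laboratory results from patient-provided sputum, saliva, nose/throat swabs and DBS samples following an exacerbation". Neither section excludes any readout.

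**What those samples are tested for.** Section 17.4.3, on exacerbation samples, lists "Anti-BCG antibody responses, as obtained from ELISAs to detect IgG, IgA and IgM responses to whole BCG organism", followed by cytokines, pathogen type, and IgG and IgA to any identified pathogen. Appendix A1.3 ties the anti-BCG assay to the blood spot itself: "DBS eluates will be used in assays to determine anti-BCG and cytokines as described in Tier 1". The Trial Summary places anti-BCG antibody among the readouts "Based on sputum, saliva, nasal swab, and DBS samples following exacerbation".

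**How the readout relates to vaccination.** Of this DBS approach, Appendix A1.1 says "we have shown that anti-BCG responses increase after vaccination".

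**The concern.** There is no placebo, so participants and treating staff know the allocation. The CAC is the step meant to keep that knowledge out of the primary outcome. If its file contains a laboratory value that tends to be higher in vaccinated participants, a reader can make a better-than-chance guess at the arm, and the blinding is weaker than claimed. What is at stake is the count of moderate to severe exacerbations, because section 8.2.1 leaves each event to an assessment of symptoms, treatment and laboratory data, and section 1.2.2 resolves disagreement by discussion. Nothing in the protocol gives anti-BCG antibody a role in deciding whether an exacerbation occurred or what caused it, so the exposure brings no stated benefit.

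**Working it through.** The point rests on reading sections together, not on a figure the protocol states.

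1. Sections 6.7 and 8.2.1 give the CAC the exacerbation DBS results, without restriction.
2. Section 17.4.3, Appendix A1.3 and the Trial Summary say the exacerbation DBS samples are assayed for anti-BCG IgG, IgA and IgM.
3. Appendix A1.1 says the anti-BCG response increases after vaccination.
4. Sections 1.2.2, 6.7 and 18.7 say the CAC does not know the allocation. No section says anti-BCG results are removed before release.

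Items 1 to 3 put a marker related to allocation within the CAC's stated inputs, which conflicts with item 4.

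**How many events could carry the result.** Section 17.5 expects data on about 1300 exacerbations and gives no derivation. From the planning rates in section 14.1:

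- mean rate = (2.25 + 1.80)/2 = 2.025 per person-year
- expected events = 804 × 2.025 = 1628, and 1300/1628 = 80%
- with the 722 participants needed after 10% loss: 722 × 2.025 = 1462, and 1300/1462 = 89%

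This is a rough ceiling. It counts sampled events, not events where the assay result is in the file when the CAC meets, and not events where the value points to the right arm.

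**How well the arm could be guessed (assumption).** The protocol gives no antibody distribution. If values were normal with equal spread and vaccination shifted the mean by d standard deviations, the best guess would be right with probability Φ(d/2):

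- d = 0.5: 60%
- d = 1: 69%
- d = 1.5: 77%
- d = 2: 84%

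Chance alone gives 50%.

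**What a guess could do (assumption).** Suppose a reader rejects a fraction f more of the events guessed to be in the BCG arm and guesses correctly with probability a. The net difference between arms is a·f − (1 − a)·f = (2a − 1)·f. For a = 0.69 the multiplier is 2 × 0.69 − 1 = 0.38. An f of 3% to 5% then becomes 1.1% to 1.9%, or 0.9% to 1.5% if 80% of events carry the result.

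**Effect on the test (assumption).** Take no true effect, 361 per arm, rate 2.25 and k = 0.36. With a net excess rejection e in the BCG arm, the standard error of the log rate ratio is √{[1/2.25 + 1/(2.25(1 − e)) + 2 × 0.36]/361}. The two-sided false-positive rate is about 6% for e = 2%, 12% for e = 5% and 34% for e = 10%, instead of 5%. At a = 0.69, reaching e = 5% would need f = 5%/0.38 = 13%, even with every event sampled.

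**The case against.** **The protocol does not itemise which DBS readouts reach the CAC.** This is true. Appendix A1.3 also describes pathogen antibody testing in matched DBS eluates, so DBS results have a legitimate use in adjudication. The terms of reference and charter, which are not shown, could limit the inputs. That makes this an unrestricted input list, not a specified act of unblinding. It does not clear the point: 6.7 and 8.2.1 expressly include DBS results, and a limit placed only in the charter would leave the primary outcome definition saying something wider.

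**The marker is weak.** Appendix A1.1 describes change within individuals over time, while 8.2.1 gives the CAC only samples taken after an exacerbation and names no baseline value. Prior BCG or TB infection is a minimisation factor (section 6.6), so it is expected in both arms. This stands. It makes the marker probabilistic, though still informative.

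**The results may arrive too late.** The CAC meets every three months (section 18.7), and no assay turnaround is given. The leak needs the result to be in the file by then, and no section says it is held back.

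**The event definition is largely objective.** Section 8.1 requires proof of prescription or admission. This limits discretion considerably but does not remove it, because 8.2.1 still calls for an assessment of symptoms and laboratory data.

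**Stronger readings that the text does not support.** A reader might infer that the CAC will know each participant's arm; the points above show otherwise. A reader might infer that the aetiology outcome is equally exposed, but section 8.2.2 names only sputum, viral and symptom data for it. A reader might want cytokines barred too, but Appendix A1.1 treats their modulation by BCG as an open question.

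**Conclusion.** The point holds in a limited form. As written, the CAC's inputs can include anti-BCG antibody measured at exacerbation, which the protocol itself says rises after vaccination. This weakens the blinding that sections 1.2.2, 6.7 and 18.7 rely on. It rests on the protocol text alone, with the CAC charter and terms of reference unseen.

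The documents give no basis for sizing a bias. The 80% (or 89%) is a rough ceiling on the share of events that could carry the result. It assumes the planning rates hold and that the sampled exacerbations are all ones the CAC would count. A reader might infer a 3% to 5% shift in the rate ratio, set against the 20% target. That figure would be an assumption, and it presumes the arm is identified correctly every time; with imperfect guessing the shift shrinks as shown. No actual bias is demonstrated. This should be fixed, preferably before the CAC reviews exacerbation DBS data, because lost blinding cannot be restored.

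**What to change.** - In sections 6.7 and 8.2.1, state that anti-BCG antibody results are withheld from the CAC, and make the broad reference to available clinical information subject to that exclusion.
- Limit laboratory inputs to pathogen results: sputum and swab PCR and culture and, if wanted, pathogen-specific antibody. This is close to the data section 8.2.2 already names for aetiology.
- Mirror the wording in the CAC charter, and have the trial office filter the laboratory extract accordingly.
- Optional companion step: the trial office masks references to trial vaccination in the records it sends to the CAC.

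The cost is wording in two sections and the charter, plus a data filter. Masking records would add some staff time. The pathogen results remain available to the CAC, and anti-BCG antibody can still be analysed in the mechanistic study.

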6.8 Informing the participant's GP and other parties

The participant's General Practitioner (GP) will be notified that they are in the STABILISE trial, using the STABILISE GP Notification Letter. No other parties outside of the trial team will be informed of the participant's entry into the trial.

7. TRIAL INTERVENTION

7.1 Trial intervention and dosing schedule

Participants will be randomised and those allocated to the intervention arm will receive the vaccine injection within 6 weeks from the date of randomisation. They will receive BCG vaccine (after reconstitution, 1 dose (0.1 ml) for adults contains Mycobacterium bovis BCG (Bacillus Calmette-Guerin), Danish strain 1331, live attenuated, 2-8 x 105 cfu). This is given as a one-off dose via the intradermal route of administration.

According to the manufacturer, the vaccine must be administered within 4 hours of opening the vial. Vials are only available to us in multi-dose vials, consequently batch delivery is required to avoid wastage. Sites can administer the allocated BCG to participants who gave consent in batches allowing them to make up one solution for delivery. We will be using administrating NHS hubs (organised by BCTU) where patients from 3-4 sites within the geographical area can travel to receive the BCG injection if they are within an hour travel. This will help to reduce the wastage of the vaccine. Patients will be reimbursed for the travel cost. Participants will be sent a letter for their vaccination appointment.

7.2 Reconstitution of the IMP

The IMP will be reconstituted by the administrating hub pharmacist or an HCP who will visually inspect the vaccine prior to administration. Each vial contains approximately 7-8 doses of the drug. To reconstitute the vaccine, 1ml of sterile water should be added to the vial and then carefully inverted a few times to re-suspend the lyophilised BCG completely, it should not be shaken. Technique for Intradermal injection

The injection site should be clean and dry. If antiseptics (such as alcohol) are applied to swab the skin, they should be allowed to evaporate completely before the injection is made. The BCG vaccine should be administered by personnel trained in the intradermal technique. The vaccine must be injected strictly intradermally in the arm, over the distal insertion of the deltoid muscle onto the humerus (approximately one third down the upper arm), as follows:

- The skin is stretched between thumb and forefinger.
- The needle should be almost parallel with the skin surface and slowly inserted (bevel upwards), approximately 2 mm into the superficial layers of the dermis.
- The needle should be visible through the epidermis during insertion.
- The injection is given slowly.
- A raised, blanched bleb is a sign of correct injection.
- The injection site is best left uncovered to facilitate healing.

7.2.1 Technical training and competency for the intervention

Some clinicians will already perform intradermal injections. However, some clinicians will not be familiar with the technique and all PI's and delegated staff performing intradermal injections will be offered remote, or where necessary, face-to-face training by a qualified TB nurse at University Hospitals Birmingham.

Written material on the technique will be provided to sites. Any clinician performing intradermal injections within the trial will be required to review the training material.

Given that intradermal injections are a simple procedure, only a self-assessment of competency and confirmation of training material review will be required. This will be recorded on a training log, which should be kept in the ISF and a copy forwarded to the STABILISE trial office. PI's will be responsible for approving trainee self-certification.

7.3 Overview of tissue sample collection

Blood samples will be collected from all participants of the trial at baseline. Some participants will be asked to provide additional blood samples at 1, 3 and 12 months. Participants will be asked to give consent to provide sputum samples, combined nasal and throat swabs at every AECOPD. Dried blood spot tests (DBS) will be completed at baseline, 3 months and 12 months follow up. Participants will also complete DBS test at every AECOPD if consented to do so.

Blood samples will be taken and processed at the local GP/NHS hospital sites. Samples will be frozen and stored at the GP/hospital site and then transported back to the Clinical Immunology Service at the University of Birmingham for longer term storage. Sample storage will be recorded in STABILISE lab file. Sputum, throat/nasal swabs and DBS tests will be sent directly to the Clinical Immunology Service at the University of Birmingham for receipt, processing and storage.

At the University of Birmingham, it is mandated that laboratories work to Good Clinical Practice.

Optional consent will be sought from participants to store any remaining blood samples after this trial for use in future research which conforms to all relevant legal, governance and ethical requirements. If consent for long term storage is not given, then these samples will be disposed of in accordance with the Human Tissue Authority's Code of Practice.

7.4 Drug interaction or contraindications

7.4.1 Permitted medication(s)/intervention(s) (including rescue medication)

There are no restrictions on permitted medication(s).

7.4.2 Concomitant medication(s)/intervention(s)

There are no restrictions on concomitant medication(s).

7.4.3 Prohibited medication(s)/intervention(s)

The are no prohibited medication(s).

7.5 Intervention modification or discontinuation

Since this trial has a one-off dose of IMP this is not applicable.

7.6 Continuation of intervention after the trial

There is no plan for repeated doses of IMP.

7.7 Intervention supply and storage

AJ Vaccines A/S are the marketing authorisation holder and manufacturer of the BCG vaccine AJV. The BCG vaccine will be sourced from a standard NHS stock supply, ring fenced for the trial. Each administering site will be responsible for maintaining the supply of BCG. Due to an international shortage of BCG, trial administering sites will be asked to purchase their BCG from UK Health Security Agency (UKHSA). UKHSA will send the trial stock of BCG vaccine directly to Trust pharmacy of the administrating hospital.

7.8 Packaging and labelling

As the IMP has a marketing authorisation in the UK, and are dispensed in their original packaging, there is a scope to reduce the labelling requirements. In compliance with Annex 13, as a minimum, trial labelling will include at least: name of sponsor and/or contract research organisation, name of trial, name of the principal investigator and name and address of the trial site.

Local sites will ensure the final labelling of the product meets the requirements above to protect the trial participant, allow full traceability, identification of the trial, identification of the product and

facilitate proper use of the IMP in accordance with Volume 4 of Good Manufacturing Practice, Annex 13 (Manufacture of investigational medicinal products 31 January 2010). BCTU will supply a template label but should sites wish to use their own label a copy should be submitted to the trial unit for Sponsor's approval prior to the opening of STABILISE at a trial site.

